6.1.2. Adverse Events

- Analysis set: Safety analysis set.
- Analysis methodology:

Adverse Events (AEs) will be graded by the investigator according to NCI CTCAE version 5.0 and coded using the MedDRA. The focus of AE summaries will be on Treatment Emergent Adverse Events (TEAEs). TEAE is defined as any adverse event that occurs during the on-treatment period, on or after the first dose of study treatment, and before the last dose of study treatment + 28 days, or the start of any other anti-cancer therapy, whichever is earlier. AEs that occurs after the on-treatment period may still be recorded in the clinical database and will be included in the AE listings, but will not be included in the AE summaries.

The number and percentage of participants who experienced any AE, serious AE (SAE), treatment related AE (i.e. related to any of the study treatment PF-07265028, or sasanlimab), and treatment related SAE will be summarized by system organ class (SOC) and preferred terms (PT) according to worst toxicity grades. The summaries will present AEs for the entire on-treatment period and for the various parts of the study (by dose level for Parts 1A and 1B, by arm for Part 2), and will not be presented by treatment cycle. In the summary tables for Parts 1A and 1B, a “Total” column, summarizing data across all dose levels, will be presented. Additionally summaries of adverse events leading to death and premature withdrawal from study treatment will be provided.

- Missing data: If AE start or stop date is missing, imputation will be performed according to [Section 5.3](#). The imputed dates will be used to determine whether the AE is to be included in the TEAE summary. The missing AE start or stop dates will be listed as is in AE listings. When the CTCAE grade is missing for an AE, the AE will be excluded from the CTCAE grade summary table.

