8.3.1. Time Period and Frequency for Collecting AE and SAE Information

The time period for actively eliciting and collecting AEs and SAEs (“active collection period”) for each participant begins from the time the participant provides informed consent, which is obtained before the participant’s participation in the study (ie, before undergoing any study-related procedure and/or receiving study intervention), through and including a minimum of 30 calendar days after the last administration of the study intervention or initiate a new systemic-anti-cancer therapy. All irAEs and treatment-related AEs must be collected for 90 days after the last dose of study intervention.

Follow-up by the investigator continues throughout and after the active collection period and until the AE or SAE or its sequelae resolve or stabilize at a level acceptable to the investigator.

For participants who are screen failures, the active collection period ends when screen failure status is determined.

If the participant withdraws from the study and also withdraws consent for the collection of future information, the active collection period ends when consent is withdrawn.

If a participant permanently discontinues or temporarily discontinues study intervention because of an AE or SAE, the AE or SAE must be recorded on the CRF and the SAE reported using the CT SAE Report Form.

Investigators are not obligated to actively seek information on AEs or SAEs after the participant has concluded study participation. However, if the investigator learns of any SAE, including a death, at any time after a participant has completed the study, and he/she considers the event to be reasonably related to the study intervention, the investigator must promptly report the SAE to Pfizer using the CT SAE Report Form.

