9.1.1.2. Incidence of AEs

Primary Estimand: Incidence of AEs estimated in the analysis population during the AE-evaluation period, defined as the time from the first dose to earliest of (28 days post last dosing date and day of new anti-cancer therapy -1 day).

- Variable: Occurrence of AEs. AEs are defined in [Appendix 3 Section 10.3](#).
- Analysis population: Safety analysis set defined as participants who receive at least 1 dose of study treatment without regard to tolerability or duration of treatment.
- Population-level summary measure: Incidence of AEs defined as the number of participants with AEs in the AE-evaluation period divided by the number of participants in the analysis population. AEs will be summarized by type, frequency, severity (as graded by NCI CTCAE version 5.0), timing, seriousness, and relationship to treatment.

9.1.1.3. OR

Estimand: The treatment effect of PF-07265028 in combination with sasanlimab assessed by ORR using the RECIST version 1.1 and irRECIST in the analysis population.

- Variable: Objective response defined as CR or PR according to RECIST v1.1 and irRECIST, from the date of first dose until the date of the first documentation of PD, death, or start of new anticancer therapy. Both CR and PR must be confirmed by

repeat assessments performed no less than 4 weeks after the criteria for response are first met.

- **Analysis population:** The response evaluable set defined as all enrolled participants who received at least 1 dose of study treatment and had adequate baseline disease assessment. Participants who discontinued early or died will be included.
- **Population-level summary measure:** ORR defined as the proportion of participants in the analysis population with OR and 2-sided 95% CI for ORR using the Clopper-Pearson/Wilson method. Participants who do not have a post-baseline tumor assessment due to early progression of disease, who receive anti-cancer therapies other than the study treatments prior to reaching a CR or PR, or who die, have PD, or stop tumor assessments for any reason prior to reaching a CR or PR will be counted as non-responders in the assessment of OR.

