2.1. Study Objectives, Endpoints, and Estimands

2.1.1. Part 1 Primary Estimands

DLT rate estimated based on data from DLT-evaluable participants during the DLT-evaluation period (Cycle 1) in Part 1.

- *Variable: Occurrence of DLTs. DLTs are defined in Protocol Section 4.3.3.*
- *Analysis population: DLT-evaluable participants defined as participants who receive at least 1 dose of study treatment, and either 1) received at least 75% of the planned doses of the study intervention and have received all scheduled safety assessments during the DLT-observation period or 2) have experienced a DLT regardless of the percentage of planned doses received. Participants without DLTs who withdraw from study treatment in the DLT-evaluation period for reasons other than treatment-related toxicity are not evaluable for DLT. All participants deemed non-evaluable for DLT may be replaced.*
- *Population-level summary measure: DLT rate defined as the number of DLT-evaluable participants with DLTs in the DLT-evaluation period divided by the number of DLT-evaluable participants in the DLT-evaluation period.*

Incidence of AEs estimated in the analysis population during the AE-evaluation period, defined as the time from the first dose to earliest of (28 days post last dosing date and day of new anti-cancer therapy -1 day).

- *Variable: Occurrence of AEs. AEs are defined in Protocol Appendix 3 Section 10.3.*
- *Analysis population: Safety analysis set defined as participants who receive at least 1 dose of study treatment without regard to tolerability or duration of treatment.*
- *Population-level summary measure: Incidence of AEs defined as the number of participants with AEs in the AE-evaluation period divided by the number of participants in the analysis population. AEs will be summarized by type, frequency, severity (as graded by NCI CTCAE version 5.0), timing, seriousness, and relationship to treatment.*

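### irAEs and treatment-related AEs are collected to 90 days after the last dose, but the SAP plans no summary of those arising after day 28 and no irAE table for any window

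*SAP*

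**What the plan says.** **Collection.** Protocol 8.3.1 runs general AE and SAE collection "through and including a minimum of 30 calendar days after the last administration of the study intervention". It then sets a longer rule for two classes of event: "All irAEs and treatment-related AEs must be collected for 90 days after the last dose of study intervention". Protocol 7.1 and 8.2.9 support this with safety follow-up to 90 days: a clinic visit at day 30 and contacts at days 60 and 90 that are remote by default.

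**Estimand.** The primary AE estimand in Protocol 9.1.1.2 ends at the earlier of 28 days after the last dose and the day before new anti-cancer therapy. SAP 2.1.1 repeats it: "Incidence of AEs estimated in the analysis population during the AE-evaluation period", with the same end point.

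**Summaries.** SAP 6.1.2 defines treatment-emergent AEs as those starting on or after the first dose and "before the last dose of study treatment + 28 days, or the start of any other anti-cancer therapy, whichever is earlier". Later AEs, where recorded, go into the listings "but will not be included in the AE summaries". On coverage it says: "The summaries will present AEs for the entire on-treatment period and for the various parts of the study". The categories it names are any AE, SAE, treatment-related AE and treatment-related SAE. SAP 6.4.2 carries the same method into Part 2.

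**Endpoint.** SAP 3.1 and 3.4 name irAEs within the primary AE endpoint of Part 1 and Part 2.

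**Two further passages bear on this.** Protocol 6.8.3.1, on supportive care for CRS, says AE summaries will cover the whole study period as well as cycles. Protocol 8.3.1.2 ends the recording of nonserious AEs when new anticancer therapy starts and keeps only SAEs going.

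**The concern.** The protocol makes 90-day collection mandatory for irAEs and treatment-related AEs, which shows that events after day 28 are thought possible and worth knowing about. The analysis plan then gives those data no planned summary. A listing shows each event, but it gives no incidence with a denominator and no worst grade by dose level or arm.

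The participants most affected are those who stop early, because the post-dose period is then a large share of their total observation. Early stopping is foreseeable: Part 2 enrolls mainly disease with primary resistance to checkpoint inhibitors, and the irAE guidance in Protocol 10.3.5 lists several events that end treatment permanently.

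Safety at the RDE and determination of the RP2D are primary Part 2 objectives, and immune-related toxicity is the first entry in the risk table of Protocol 2.3.1. At stake is whether the tabulated safety profile of the combination shows the delayed immune-related events that the trial takes the trouble to collect.

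**Working it through.** The plan gives no figure to reproduce. The check compares the two windows.

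**Inputs.** Collection of irAEs and treatment-related AEs: 90 days after last dose (Protocol 8.3.1). Collection of other AEs: at least 30 days (same section). Summary window: 28 days, or less if new therapy starts (SAP 6.1.2; Protocol 9.1.1.2). Cycle length: 28 days. Treatment: up to 24 months (Protocol 4.1). Part 2A cohort: up to 40 (Protocol 9.5.2).

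**Step 1: days outside every summary, no new therapy.**
- irAEs and treatment-related AEs: 90 − 28 = 62 days, and 62/90 = 68.9% of the post-dose collection window.
- Other AEs: 30 − 28 = 2 days.

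**Step 2: effect of new therapy.** If it starts t days after the last dose, with t below 28, the summary closes at about t. Under the 90-day rule read literally, 90 − t days are then unsummarized, which exceeds 62. Under Protocol 8.3.1.2, nonserious recording also stops at t, so the nonserious gap is nil and only SAEs remain. If t lies between 28 and 90, the nonserious gap under 8.3.1.2 is t − 28. The size of the gap therefore depends on which section governs.

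**Step 3: who is affected most.** Assume daily oral dosing to the end of the stated period and no new therapy. Share of collected time that is summarized = (last dose day + 28)/(last dose day + 90).
- One cycle: (28 + 28)/(28 + 90) = 56/118 = 47%.
- Two cycles: (56 + 28)/(56 + 90) = 84/146 = 58%.
- 24 months, about 730 days: 758/820 = 92%.

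**Step 4: events.** The documents give no rate of delayed irAEs, so the number of events outside the tables cannot be computed. For scale only, assume a share q of participants whose only irAE starts after day 28. In a cohort of 40 the expected number is 40q, and the chance of at least one is 1 − (1 − q)^40:
- q = 1%: 0.4 expected, 33%.
- q = 2%: 0.8 expected, 55%.
- q = 5%: 2 expected, 87%.
- q = 10%: 4 expected, 98.5%.

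The range of q is an assumption.

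**The case against.** The strongest reply is that the 28-day window is the prespecified primary estimand. Protocol 9.1.1.2 and SAP 2.1.1 agree on it, and SAP 6.1.2 applies essentially the same cut-off. A reader might infer that part of the primary safety endpoint is being dropped, or that the SAP departs from the protocol's estimand. The documents do not support that: nothing inside the estimand is omitted, and collecting safety data for longer than they are summarized is not in itself a contradiction. This part of the reply stands in full.

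A reader might also take 69% as the share of toxicity that goes unreported. It is a share of post-dose calendar days. Everything on treatment, for up to 24 months, is summarized. Nor can a fall in irAE incidence be read off. A participant whose first irAE is early and whose worst is late would still count in an incidence table; only the grade would change. In any case SAP 6.1.2 specifies no irAE incidence table from which a figure could fall.

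Third, a distorted RP2D does not follow. Protocol 4.3.5 bases the RP2D on an integrated assessment, Protocol 4.2.2 and 9.3.5 provide for ongoing review of individual and summary safety data, and late events remain in the listings.

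Finally, later data are weaker: the day-60 and day-90 contacts are remote by default, follow-up will be unequal, and attribution is harder after new therapy. That limits how a 90-day table should be read. It does not explain why mandatorily collected data have no planned summary.

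**Conclusion.** The concern holds as a reporting gap outside the primary estimand. Under the SAP text available, some of which is redacted, irAEs and treatment-related AEs arising after the 28-day cut-off enter no incidence or worst-grade table, and irAEs have no dedicated summary in any window. The gap is up to 62 days for a participant who starts no new anti-cancer therapy, and it is proportionally largest for those who stop early. The number of events cannot be derived from the documents, so no understatement of incidence should be quoted.

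Two textual conflicts also need settling. Protocol 6.8.3.1 promises whole-study and by-cycle AE summaries, whereas Protocol 9.1.1.2 ends the AE-evaluation period at 28 days and SAP 6.1.2 restricts summaries to the on-treatment period and rules out presentation by cycle. The 90-day rule in Protocol 8.3.1 makes no exception for new therapy, whereas 8.3.1.2 stops nonserious recording at that point.

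In an uncontrolled, descriptive Phase 1 study this is a worthwhile, inexpensive improvement. It is not a fault in the primary analysis.

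**What to change.** Keep the 28-day treatment-emergent tables as the primary estimand. Add to SAP 6.1.2, applying to both parts, a supplementary summary on the safety analysis set of:
- irAEs, and treatment-related AEs and SAEs, by preferred term and worst grade, from first dose to 90 days after last dose;
- nonserious events cut at the start of new anti-cancer therapy, in line with Protocol 8.3.1.2;
- SAEs after new therapy shown separately.

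State how an irAE is identified for this table, and report how many participants reached the day-30, day-60 and day-90 contacts so that unequal follow-up is visible.

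In the protocol, reconcile the AE-summary sentence in 6.8.3.1 with 9.1.1.2 and SAP 6.1.2, and reconcile 8.3.1 with 8.3.1.2 on what is recorded after new therapy begins.

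The cost is one or two tables from data the protocol already requires, with no new visits and no change to the primary estimand. The drawback is that the later part of the window rests on remote contacts and uneven follow-up, with less certain attribution, so the table should be labelled supplementary.

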Dose levels that have cleared the DLT period in Part 1 may be expanded up to 10 participants PF-07265028 administered as monotherapy or in combination sasanlimab at or below the MTD. Expansion of dose levels will be based on evolving clinical data (including safety, PK, and PD) to explore activity and help identify the RDE of the monotherapy and/or combination in Part 2.

Please see below for intra-participant dose escalation rules and rules for crossover from Part 1A to Part 1B.

- To minimize the risk that an individual participant may be exposed to a sub-therapeutic dose, intra-participant dose escalation of PF-07265028 in Part 1 to the maximal dose level that has previously been determined to be safe (based on BLRM) may be allowed if the protocol required safety assessments for the previous treatment cycle have been performed and as follows:
 1. Participant has completed 2 cycles of treatment at the current dose level; or if disease progression occurs.
 2. No Grade ≥ 3 treatment-emergent toxicities were experienced at the participant's current dose level.
 3. If a clinical rationale is provided by the investigator and approved by the sponsor.
- In Part 1A (monotherapy dose escalation) participants with SD after 2 cycles of treatment, and additionally participants with a RECIST response of PR or CR, who then experience PD, may rollover to the combination cohort regardless of prior PDx status.

Participants in Part 1 must have recently obtained archival tumor tissue available (collected within 6 months prior to screening). If the archival sample is older than 6 months, the participant must consent to undergo a fresh pre-treatment biopsy during the screening period. If a new biopsy represents a significant safety risk in the opinion of the investigator, the participant may be considered for enrollment with archival samples only after discussion with the sponsor.

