5.2. General Methods

Whilst every effort has been made to pre-specify all analyses in this statistical analysis plan, CCI, the analyses and the reasons for them will be detailed in the clinical study report (CSR).

Unless otherwise specified, the baseline value is defined as the value collected at the time closest to, but prior to, the start of study drug administration in the first cycle. All data will be categorized based on the scheduled visit at which it was collected. These visit designators are predefined values that appear as part of the visit tab in the case report form (CRF).

The data will be summarized by dose level, defined by the initial dose of the study intervention administered to participants. If a dose level has more than 1 cohort, data from these cohorts will be combined. DLT rates at the study dose levels will be presented via mean and medians and a Bayesian credible interval based on the posterior density from the full probability model. This information will also be used for the dose level review meetings (DLRM) to guide the dose escalation.

For Part 1A and Part 1B, when there are multiple dose levels, in addition to data presentation by dose level, the overall summary combining all dose levels may also be presented.

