6.1.3. Laboratory abnormalities

- Analysis set: Safety analysis set.
- Analysis methodology:

Laboratory tests in this study include several panels: hematology, chemistry, serology, coagulation, urinalysis, and pregnancy test.

The frequency and percentage of participants who experienced laboratory test abnormalities will be summarized according to worst toxicity grade (based on NCI CTCAE version 5.0) observed for each laboratory assay. Summaries of laboratory

tests results by visit may be provided. Summaries for change from baseline and percent change from baseline for the laboratory tests may be provided, if deemed necessary. Shift tables may be provided for selected laboratory tests.

The summaries will be presented for the entire on-treatment period and for the various parts of the study (by dose level for Parts 1A and 1B, by arm for Part 2), and will not be presented by treatment cycle.

Hematology, serology, and coagulation lab results can be combined into one summary output. Separate summaries will be created for chemistry tests. Urinalysis and pregnancy tests will not be summarized and will only be listed in data listings. Shift tables may be provided for selected laboratory tests.

- Missing data: Intermediate missing values (ie, values collected between baseline and the last study measurement) will not be imputed.

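### Part 1 AE and laboratory tables count events after intra-participant escalation under the lower starting dose, and the SAP does not say where events after rollover to sasanlimab belong

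*SAP*

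**What the plan says.** SAP 5.2 sets the grouping rule for all summaries: "The data will be summarized by dose level, defined by the initial dose of the study intervention administered to participants". SAP 6.1.2 reports AEs by worst grade: "The summaries will present AEs for the entire on-treatment period and for the various parts of the study". The split is by dose level in Parts 1A and 1B, with none by treatment cycle. A Total column, "summarizing data across all dose levels, will be presented". SAP 6.1.3 uses the same layout for laboratory abnormalities: "The summaries will be presented for the entire on-treatment period and for the various parts of the study". For AEs, the on-treatment period runs from first dose to 28 days after last dose, or to another anti-cancer therapy if earlier. Neither section replaces the rule in 5.2.

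Protocol 4.1.1 allows "intra-participant dose escalation of PF-07265028 in Part 1 to the maximal dose level that has previously been determined to be safe", on condition that no Grade 3 or higher "treatment-emergent toxicities were experienced at the" participant's current dose. Part 1A participants who meet certain disease-status conditions "may rollover to the combination cohort regardless of prior PDx status". On group size, the same section says: "Dose levels that have cleared the DLT period in Part 1 may be expanded up to 10 participants". SAP 6.1.1 plans cohorts of about 3.

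The SAP deals with rollover in two places. SAP 6.1.1 leaves rolled-over participants out of the Part 1B DLT assessment. SAP 6.2.3 cuts their response data at the crossover date in its primary method and adds post-crossover data to Part 1B in a second analysis.

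**The concern.** AEs and laboratory abnormalities are Part 1 primary endpoints, and the by-dose tables are their main display. Under the initial-dose rule, a toxicity that first appears at a higher dose is shown at the lower dose where the participant began and is missing from the dose at which it occurred. With groups this small, one participant can make the lower dose look more toxic than the higher one.

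Rollover adds a separate problem. If post-rollover events stay with the initial dose, toxicity during sasanlimab treatment appears in a monotherapy group. The SAP also does not say whether a rolled-over participant enters the Part 1B safety denominator.

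This matters beyond the MTD, because protocol 4.3.5 bases the RP2D on an integrated assessment that includes safety and may place it below the MTD.

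**Working it through.** The plan states no figure on this point, so there is none to reproduce. The check is a reading of the rules followed by simple arithmetic.

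**1. Where a post-escalation event goes.** Dose level is the initial dose (SAP 5.2). The window covers all on-treatment time (SAP 6.1.2, 6.1.3) and does not end at escalation. The event is therefore counted at the starting dose. On the provisional levels in protocol Table 7 (25, 50, 80 and 125 mg QD), the dose taken could be up to 125/25 = 5 times the dose shown, if all levels were cleared.

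**2. Effect of one participant with a first Grade 3 or higher event.** The escalation condition means such a participant should not already be in the Grade 3 or higher count, so the shift is 1/n. Intervals are Clopper-Pearson 95%, the method in SAP 5.2.1.

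| Group size | Without the event | With the event | Shift |
|---|---|---|---|
| 3 | 0/3 = 0% (0 to 70.8%) | 1/3 = 33.3% (0.8 to 90.6%) | 33.3 points |
| 10 | 0/10 = 0% (0 to 30.8%) | 1/10 = 10.0% (0.3 to 44.5%) | 10.0 points |

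**3. Reversal of order.** Suppose 3 participants start at each of two adjacent doses, one escalates from lower to higher, and that participant has the only event, at the higher dose.

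- By dose at onset: lower 0/3 = 0%; higher 1/(3+1) = 25%.
- By initial dose, as in the SAP: lower 1/3 = 33.3%; higher 0/3 = 0%.

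**4. Any-grade rows.** The participant may already be counted. With q the chance of that, the expected shift in a group of 3 is (1 − q)/3: 25.0 points at q = 0.25, 16.7 at 0.50, 8.3 at 0.75 and 0 at q = 1. The values of q are assumed.

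**5. Expected shift for Grade 3 or higher.** The formula is k × p / n, where k is the number who escalate, n the group size and p the post-escalation risk. The documents give neither k nor p. As an assumption, p runs from 0.05 to 0.40.

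| k | n | Expected shift |
|---|---|---|
| 1 | 3 | 1.7 to 13.3 points |
| 2 | 3 | 3.3 to 26.7 points |
| 2 | 10 | 1.0 to 8.0 points |

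**6. Rollover.** Two readings are open. Presentation by study part and dose level could put combination-period events in Part 1B. A literal use of initial dose puts them in a Part 1A group and in the Part 1A Total. On the literal reading, one event adds up to 1/3 = 33.3 points to a Part 1A group of 3. It adds up to 1/30 = 3.3 points to the Part 1A Total, taking the approximately 30 participants in protocol 9.5.1. The start of sasanlimab does not clearly end the on-treatment period, because protocol section 6 counts sasanlimab as study intervention and the period ends only at other anti-cancer therapy.

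**The case against.** The strongest reply is that grouping by initial dose is a disclosed convention that fits the estimand. Protocol 9.1.1.2 and SAP 2.1.1 count AEs from first dose to 28 days after last dose or new anti-cancer therapy, and escalation does not stop that clock. Dose at onset is no neutral standard either: the 1/4 in the worked case mixes participants who started at the higher dose with one who had earlier exposure and was selected for tolerating it, and delayed events would be charged wholly to the later dose. This stands, and is why the initial-dose table should stay primary and the added tables should be descriptive.

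A second point is that the escalation condition speaks of toxicities while the AE table counts AEs of any cause. If toxicities excludes disease-related events, an escalating participant could already be in the Grade 3 or higher count. The net addition in step 2 therefore holds when the condition covers all treatment-emergent events.

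Third, the wide intervals show that groups of 3 cannot rank doses under any rule, and stopping requires at least 6 participants at the MTD/RDE. Escalation and rollover are optional. Dose decisions also draw on dose level review meetings and individual data, and the AE and dosing listings (SAP 6.1.2, 6.8.3) allow reattribution by hand. All true; these points limit the consequence, but no planned table shows the attribution.

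Finally, protocol 6.8.3.1 describes AE summaries for Cycle 1 and for later cycles, which SAP 6.1.2 drops. Restoring them would largely keep Cycle 1 free of the problem, since escalation normally follows two cycles, but would not tie later events to a dose. Placing rollover events in Part 1B is a natural reading, but the SAP does not state it.

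**Conclusion.** The concern holds. Followed exactly, the SAP counts post-escalation AEs and laboratory abnormalities under a lower dose than the one at which they arose, and it leaves the placement of post-rollover events open. One such Grade 3 or higher event shifts a group of 3 by 33 points and a group of 10 by 10 points, and in the two-dose example it reverses the order of the doses. Average shifts depend on assumed escalation and event rates. The rollover figures apply only on the literal initial-dose reading. Cycle 1 DLT and MTD data are unaffected: escalation requires the previous cycle's safety assessments, and rolled-over participants are excluded from the Part 1B DLT assessment. This should be changed, but it does not undermine the dose-escalation design.

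**What to change.** Keep the initial-dose table over the AE-evaluation period as the primary estimand table, and add one sentence saying where it places AEs and laboratory data after rollover.

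In SAP 6.1.2 and 6.1.3, add a supplementary Part 1 summary that cuts each participant's data at first intra-participant escalation and at the first sasanlimab dose after rollover. Show post-escalation and post-rollover events in separate columns with their own denominators. State that in this summary post-rollover events are not reported as Part 1A monotherapy events, in line with the crossover cut in SAP 6.2.3.

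The cost is a few SAP sentences, one AE table and one laboratory table. AE dates and daily dose by dosing period are already collected and listed. The estimand is unchanged while the cuts stay in the supplementary tables; applying them to the primary table would shorten its AE-evaluation period and require amending protocol 9.1.1.2 and SAP 2.1.1. The added columns will be small and drawn from participants selected for tolerating the earlier dose, so they should be labelled descriptive.
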